5.3.3.4 WHO OSCI

The WHO OSCI has values ranging from 0 to 8 as shown in [Table 6](#).

Table 6 WHO Ordinal Scale for clinical Improvement

Participant State	Descriptor	Score
Uninfected	No clinical or virological evidence of infection	0
Ambulatory	No limitation of activities	1
	Limitation of activities	2

Participant State	Descriptor	Score
Hospitalized – Mild disease	Hospitalized, no oxygen therapy	3
	Oxygen by mask or nasal prongs	4
Hospitalized – Severe Disease	Non-invasive ventilation or high flow oxygen	5
	Intubation and mechanical ventilation	6
	Ventilation + additional organ support	7
Dead	Death	8

The WHO OSCI will be recorded daily in the eCRF while participants remain in hospital. Once discharged, the WHO OSCI will be derived from questions 1 and 2 of the daily COVID-19 diary using the rules defined in [Table 7](#).

Table 7 Derivation of WHO OSCI using the Outpatient Daily Covid-19 diary

Question 1: Overall, how severe were your COVID-19 symptoms today?	Question 2: How much did your COVID-19 symptoms interfere with your usual activities today?	WHO OSCI Score
No COVID-19 symptoms today	Any response	0
Mild, moderate, severe or very severe	Not at all	1
Mild, moderate, severe or very severe	Somewhat or Very much	2

For participants who report question 1 as “No COVID-19 symptoms today” and a return to their usual activities (Q3) for 2 days in a row do not need to complete the COVID-19 diary on subsequent days. If this condition is met, the missing WHO OSCI score will be imputed as 0 for any remaining study days up to and including Day 42.

Note that participants who are discharged on home oxygen will still be considered as having WHO OSCI score =2 as the participant state is considered before the descriptor in [Table 6](#).

For participants who die, the WHO OSCI score will be imputed to 8 for all remaining study days after death.

WHO OSCI scores that are missing for reasons other than death or full recovery of symptoms will not be imputed.

For the secondary endpoint looking at whether participants remained at or below their baseline WHO OSCI score at Days 4, 7, 10, 14, 21 and 42, participants who show an increased score and then return to their baseline score (or lower) will not be considered as having met the criterion for this endpoint. Only participants who have not reported a score above their baseline score on any day prior to the endpoint day will be considered as having met the endpoint for that day.

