5.3.3.7 Number of Days Requiring Oxygen Therapy

For participants who are discharged with ongoing oxygen therapy, any changes to their oxygen therapy are to be reported in the participant diary they complete daily. This data will be transcribed to the oxygen therapy page of the main CRF.

Each study day will be flagged as with or without oxygen therapy based on the start and stop dates for relevant records in oxygen therapy page. For example, if a record for oxygen therapy is shown as starting on Day 2 and ending on Day 6 then Days 2-6 inclusive will all be flagged as with oxygen therapy.

Number of days with oxygen therapy will be reported for the following intervals:

- Days 1-14
- Days 1-28
- Days 1-42

For each interval, the percentage of days with oxygen therapy will be calculated, using the number of days in the interval prior to death or premature withdrawal as the denominator.

For participants who die or withdraw prematurely from the study, a sensitivity variable will be created which counts study days after death/early withdrawal as 'with oxygen therapy' up to Day 42.

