7.4.2 Planned Schedule of Interim Analyses

Interim analyses are planned after 10, 20, 30, 40 and 60 participants have completed 7 days follow-up after their last dose (Day 21 for participants who complete dosing as scheduled).

At all interim analyses, the DMC will review safety and study disposition data to assess the safety of the interventions and to monitor the overall conduct of the study. Safety review will focus on the number and details of severe and serious adverse events, gastrointestinal (GI) events of any grade and laboratory data which meets the criteria for potentially clinically important (PCI).

At the second interim, after 20 participants have completed 7 days of follow-up after their last dose, the DMC will also specifically address the question of recruitment can be opened to participants aged >65 years.

At the final interim, after 60 participants have completed 7 days of follow-up after their last dose, the DMC will also review the efficacy data in order to make a recommendation on whether recruitment should be extended to a further 40 participants.

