9.3.3 WHO OSCI Score

9.3.3.1 Estimands

The endpoints will be recorded (inpatients) or derived (outpatients) WHO OSCI score at Days 4, 7, 14, 21 and 42. Population summary methods will be:

- Percentage of participants at each level of the WHO OSCI score
- Percentage of participants with each possible shift from Baseline in WHO OSCI score
- Percentage of participants remaining at their baseline WHO OSCI score (or lower)

- Percentage of participants reporting each level of WHO OSCi score at their worst post-baseline day

The intercurrent event strategy for these estimands is described in [Table 11](#).

Table 11 Intercurrent Event Strategies for the WHO OSCi Score Secondary Estimands

Intercurrent event	Strategy to account for intercurrent event
Death prior to the study day of interest	Composite WHO OSCi score of 8 will be carried forward to all further study days
Discharge prior to the study day of interest	Treatment policy The WHO OSCi score will be derived from the participant daily diary using the rules in Section 5.3.3.4
Treatment discontinuation before the study day of interest and no other experimental treatment not considered standard of care initiated	Treatment policy WHO OSCi score used as recorded for inpatients or derived for outpatients from the participant daily diary using the rules in Section 5.3.3.4
Withdrawal from the study due to initiating other experimental treatment not considered standard of care before the study day of interest	While-on-treatment Participants will be excluded from the analysis at that study day

Data missing for reasons other than an intercurrent event as detailed above will not be imputed.

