9.3.4 Overall Survival and Intubation and Mechanical Ventilation Free Survival

9.3.4.1 Estimands

The endpoint will be time to event in days as defined in [Section 5.3.3.5](#). The population summary measure of interest will be the hazard ratio for the EDP1815 group compared to the placebo group.

The intercurrent event strategy for these estimands is described in [Table 12](#).

Table 12 Intercurrent Event Strategies for Overall Survival and Intubation and Mechanical Ventilation Free Survival Secondary Estimands

Intercurrent event	Strategy to account for intercurrent event
Discharge prior to Day 42	Treatment policy Participants actual status will be used
Treatment discontinuation before Day 14 without withdrawal from the study	Treatment policy Participants actual status will be used
Withdrawal from the study	While-on-treatment Participants will be censored at the time of withdrawal from the study.

For the interim analysis presented at the DMC meeting when 60 patients have completed 21 days in the study, subjects who are still ongoing and have not met the criteria for the relevant event will be censored at the date of the data cut.

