14.2.3.2.3	Analysis of Percentage Change from Baseline in S/F Ratio at Days 4, 7, 10 and 14, Sensitivity Analysis Using MMRM approach	ITT		Only produced if >10% drop-out before D14
14.2.3.2.4	Analysis of Percentage Change from Baseline in S/F ratio at Days 4, 7, 10 and 14, Sensitivity Analysis Accounting for Use of New SOC	ITT		Only produced if a new SOC is introduced during the study
14.2.4.1	Summary and Analysis of WHO OSCI score at Days 4, 7, 14, 21 and 42	ITT	Yes, summary only	DMC-Unblinded
14.2.4.2	Shift Table of Changes from Baseline in WHO OSCI Score at Days 4, 7, 14, 21 and 42	ITT	Yes	DMC-Unblinded
14.2.4.3	Summary of Participants Remaining at or Below Their Baseline WHO OSCI Scale Score at Days 4, 7, 14, 21 and 42	ITT	Yes	DMC-Efficacy
14.2.4.4	Summary and Analysis of Maximum WHO OSCI Score Reported	ITT	Yes, exclude p-value	DMC-Efficacy
14.2.5.1	Summary and Analysis of Overall Survival	ITT	Yes, exclude Hazard ratio, CI and p-value	DMC-Efficacy
14.2.5.2	Summary and Analysis of Overall Survival, Sensitivity Analysis Accounting for Use of New SOC	ITT		
14.2.6.1	Summary and Analysis of Intubation and Mechanical Ventilation Free Survival	ITT	Yes, exclude Hazard ratio, CI and p-value	DMC-Efficacy

Number	Title	Population	Early Stop	Programming notes ¹
14.2.6.2	Summary and Analysis of Intubation and Mechanical Ventilation Free Survival, Sensitivity Analysis Accounting for Use of New SOC	ITT		
14.2.7	Summary and Analysis of Time to Discharge	ITT	Yes, exclude Hazard ratio, CI and p-value	DMC-Efficacy
14.2.8	Summary and Analysis of Time to SpO ₂ ≥94% on Room Air Without Further Requirement for Oxygen Therapy	ITT	Yes, exclude Hazard ratio, CI and p-value	DMC-Efficacy
14.2.9	Summary and Analysis of Time to Recovery from Onset of Symptoms	ITT	Yes, exclude Hazard ratio, CI and p-value	DMC-Efficacy
14.2.10	Summary of Number of Days Requiring Oxygen Therapy	ITT	Yes	DMC-Efficacy
14.2.11	Summary of Number of Days with Pyrexia	ITT	Yes	DMC-Efficacy
14.2.12	Summary of Maximum Daily Temperature	ITT	Yes	DMC-Efficacy
14.2.13	Summary of Maximum and Minimum Daily SpO ₂ values	ITT	Yes	DMC-Efficacy
14.2.14	Summary of Change from Baseline in Cytokine levels at Days 4 and 7	ITT		
14.2.15	Summary of Change from baseline in Inflammatory Response Markers at Days 4 and 7	ITT	Yes	
14.2.16	Exploratory Analysis of Potential Predictor-Treatment Interactions	ITT		

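### At the DMC interims the WHO OSCI carry-forward has no data-cut limit, so Day 42 is filled in early for the recovered and the dead and left blank for those still ill

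*SAP*

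**What the plan says.** SAP 5.3.3.4 has three rules for a missing OSCI score.

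- Recovered outpatients (two consecutive days without symptoms and with a return to usual activities) stop the diary, and "the missing WHO OSCI score will be imputed as 0 for any remaining study days up to and including Day 42".
- For deaths, "the WHO OSCI score will be imputed to 8 for all remaining study days after death". SAP 9.3.3.1, Table 11, repeats this: a "score of 8 will be carried forward to all further study days".
- For everyone else, "WHO OSCI scores that are missing for reasons other than death or full recovery of symptoms will not be imputed".

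None of these mentions a data cut. SAP section 8 bases percentages for categorical measures on the non-missing sample size.

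On timing, SAP 7.4.2 states: "Interim analyses are planned after 10, 20, 30, 40 and 60 participants have completed 7 days follow-up after their last dose". It equates this with Day 21 for participants who complete dosing.

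On content, SAP 16.2.1 flags Table 14.2.4.1, "Summary and Analysis of WHO OSCI score at Days 4, 7, 14, 21 and 42", and the matching shift table 14.2.4.2 as DMC-Unblinded. SAP section 16 defines that flag as unblinded output for all DMC meetings. SAP 9.3.3.2 adds a CMH comparison of the arms at each of these days.

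For the time-to-event endpoints at the 60-participant meeting, the SAP does limit the data: ongoing participants without the event "will be censored at the date of the data cut" (SAP 9.3.4.1, and again in 9.3.5.1). There is no counterpart for OSCI.

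**The concern.** At a meeting triggered at Day 21, the counted participants may be three weeks short of Day 42. Applied literally, the rules decide who appears in the Day 42 column by outcome. A participant who has recovered enters as 0, which is a forecast of no relapse. A participant who has died enters as 8, which is a true outcome. A participant still in hospital or symptomatic is blank and leaves the denominator. The death count is right, but the percentage is not.

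At the first four meetings, Tables 14.2.4.1 and 14.2.4.2 are the only efficacy tables flagged for the DMC. The survival, discharge and S/F tables carry the DMC-Efficacy flag and appear only at 60 participants. At every meeting the committee may be judging whether EDP1815 is potentially detrimental (SAP 7.4.4). Because the share still ill depends on recovery speed, two arms with equal mortality can show unequal Day 42 death percentages.

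**Working it through.** **Timing.** The SAP's own figure reproduces: last dose Day 14 + 7 days = Day 21. The gap to Day 42 is 42 − 21 = 21 days.

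**How many are short of Day 42.** Accrual is not stated, so assume 60 participants enrol evenly over T days, with spacing g = T/60. The interim for the k-th participant falls 20 days after that participant's enrolment (study Day 21). Participant i has reached Day 42 if enrolment + 41 days is no later than this, that is, if (k − i) × g ≥ 21. The number of the k not there is the smaller of k and 21/g rounded up.

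| T (days) | g (days) | 21/g, rounded up | Short of Day 42 at k = 10 | Short of Day 42 at k = 60 |
|---|---|---|---|---|
| 60 | 1 | 21 | 10/10 = 100% | 21/60 = 35% |
| 90 | 1.5 | 14 | 10/10 = 100% | 14/60 = 23% |
| 120 | 2 | 11 | 10/10 = 100% | 11/60 = 18% |
| 180 | 3 | 7 | 7/10 = 70% | 7/60 = 12% |
| 240 | 4 | 6 | 6/10 = 60% | 6/60 = 10% |

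At interims before the last, participants enrolled after the k-th are also short of Day 42.

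**What the column shows (illustrative counts).** Take 20 participants, none at Day 42: 12 recovered, 2 dead, 6 still ill. The column has n = 12 + 2 = 14 and reads 12/14 = 85.7% recovered, 2/14 = 14.3% dead, 0% still ill. Status at the cut is 12/20 = 60%, 2/20 = 10% and 6/20 = 30%.

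**By arm (illustrative).** Ten per arm, none at Day 42, one death in each.

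| | Recovered / dead / still ill | Day 42 column: recovered | Day 42 column: dead | Day 42 column: still ill |
|---|---|---|---|---|
| Arm A | 7 / 1 / 2 | 7/8 = 87.5% | 1/8 = 12.5% | 0% |
| Arm B | 3 / 1 / 6 | 3/4 = 75% | 1/4 = 25% | 0% |

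Equal mortality appears doubled in arm B. The real contrast in those still ill (20% against 60%) vanishes, and the 40-point gap in recovery (70% against 30%) shrinks to 12.5 points.

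**Size against the eventual Day 42 result.** A simulation (3,000 runs per scenario) assumed one participant per day, 8% mortality, a median of 8 days to discharge and then a median of 10 days to recovery. None of these comes from the documents. Percentages are recovered / symptomatic outpatient / hospitalised / dead.

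| Interim | Day 42 under the SAP rule | Assumed truth |
|---|---|---|
| 20 participants | 89.3 / 0 / 0 / 10.7 | 85.4 / 6.3 / 0.3 / 8.0 |
| 20 participants, median recovery 20 days | 82.3 / 0 / 0 / 17.7 | 65.8 / 25.9 / 0.3 / 8.0 |
| 60 participants | 86.7 / 4.5 / 0.2 / 8.6 | 85.2 / 6.4 / 0.3 / 8.1 |

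At 60 participants the errors are 86.7 − 85.2 = 1.5 points for recovery and 8.6 − 8.1 = 0.5 points for death. At two participants per day they were 88.6 − 85.3 = 3.3 and 9.1 − 8.1 = 1.0.

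**Day 21.** The same mechanism acts on Day 21 only if participants not yet at Day 21 are tabulated. SAP 8.1 points that way, since interim disposition counts participants still on treatment. In the first scenario at the 20-participant interim, Day 21 read 49.8 / 36.8 / 6.5 / 6.8 against 45.2 / 41.9 / 7.5 / 5.4. At 60 participants there was no error when all completed dosing.

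**Effect of the fix.** With each column restricted to participants whose day has come, Day 42 at 60 participants (one per day) has n = 39 and gives 85.2% recovered and 8.1% dead, the assumed truth. At 10 and 20 participants it has n = 0 and is not shown.

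**The case against.** The best defence is that a day that has not happened is not plainly a missing score. The rule explains why recovered participants stop the diary and was probably written for completed follow-up, and a careful programmer might filter by date. SAP 7.4.6 also refers to the DMC charter for the content of meetings. This stands in part: the defect is what the text yields when followed literally, and the charter is not available. But SAP 9.3.4.1 and 9.3.5.1 put cut rules for other endpoints in the SAP itself, and SAP 7.4.5 gives the unblinded interim work to a separate team, for whom no OSCI filter is written.

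The DMC also has other information. The same tables show Days 4, 7 and 14, and the participant-level OSCI listing (16.2.6.2) and disposition with ongoing counts go to every meeting. SAP 7.4.2 centres safety review on adverse events and laboratory values. A reader might infer that longer hospitalisation in one arm would be hidden from the committee. The documents do not support that: the Day 42 column would hide it, but these other outputs would not.

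A reader might also infer that the decision to extend to 100 is materially biased. That decision is taken only at 60 participants, where the error is probably small, time-to-event analyses censored at the cut are supplied, and SAP 7.4.3 sets no numerical rule.

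For oxygen days, SAP 5.3.3.7 forms percentages "using the number of days in the interval prior to death or premature withdrawal as the denominator", again without a cut. It is tempting to say that an ongoing participant's future days count as oxygen-free. For someone on oxygen every day to Day 21, that gives 21/42 = 50%. But the SAP does not say how an oxygen record with no stop date is flagged after the cut, and flagging it to the end of the interval gives 42/42 = 100%. What is shown is an unspecified rule. The main pyrexia percentage already uses days with a recorded temperature (SAP 5.3.3.8) and needs no change.

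**Conclusion.** The point holds for the Day 42 columns of Tables 14.2.4.1 and 14.2.4.2 at the interims. Read as written, SAP 5.3.3.4 with the section 8 denominator fills Day 42 selectively by outcome. Compared with status at the cut, the recovered and dead percentages are too high and the still-ill percentage too low, unequally between arms if recovery speed differs. Both percentages also exceeded the eventual Day 42 values in every scenario run, though for recovery that direction is not guaranteed when deaths come early and recoveries late.

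The effect is largest at the early meetings and probably small at 60 participants. These sizes rest on assumed accrual and outcomes. The Day 21 effect is smaller, confined to early interims, and depends on who is tabulated; at 60 participants it is nil or limited to those who stopped dosing early. The final analysis is not affected, and all analyses are declared descriptive. The change is worth making because these tables are unblinded, by arm, and the only efficacy tables at the first four meetings.

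**What to change.** Add to SAP 5.3.3.4, with a cross-reference in 7.4, that for interim outputs:

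- the carry-forward of 0 and of 8 stops at the data cut;
- each OSCI study-day column includes only participants whose Day X, counted from their start of treatment, falls on or before the cut, whatever their outcome, with that number as the denominator.

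As a secondary change in SAP 5.3.3.7, end each participant's interval for the interim oxygen-day percentage at the earliest of death, withdrawal and the data cut, and flag open oxygen records only to that point. The continuous-oxygen example then gives 21/21 = 100%.

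The cost is one SAP paragraph and a date filter in the interim programs. The downside is small or empty Day 42 columns at early interims, which correctly reflects what has been observed.

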4.2 Endpoints

Table 1 List of endpoints associated with each study objective

Objectives	Endpoints
Primary	

• To evaluate the effect of EDP1815 on pulmonary function as measured by the change in S/F Ratio	
• Change from baseline to the lowest S/F ratio measured in days 1-14

Objectives	Endpoints
Secondary	

 To evaluate the effect of EDP1815 on the development and severity of complications of COVID-19 infection 	
 Change in S/F ratio at days 4, 7, 10 and 14/discharge day. Percentage change in S/F ratio at days 4, 7, 10 and 14/discharge day. Percentage of participants at each level on the WHO OSCI score at days 4, 7, 14, 21 and 42. Percentage of participants with shifts from each level of the WHO OSCI score at baseline at days 4, 7, 14, 21 and 42. Percentage of participants remaining at their baseline score on the WHO OSCI (or lower) at days 4, 7, 14, 21 and 42. Percentage of participants reporting each level of the WHO OSCI score at their worst post-baseline day. The time in days spent at each participant's worst reported WHO OSCI score (excluding death). Intubation and mechanical-ventilation free survival, defined as the time in days from start of treatment to first occurrence of a WHO OSCI score of 6 or more. Overall survival, defined as the time in days from start of treatment to death by any cause Number of days requiring oxygen therapy. Number of days with pyrexia $\geq 38^{\circ}\text{C}$. Maximum daily temperature. Minimum SpO₂ level. Maximum SpO₂ level.

 To evaluate the effect of EDP1815 on length of hospitalization and recovery in participants with COVID-19 	
 Time to discharge, defined as the time in days from start of treatment to first occurrence of a WHO OSCI score of 2 or less. Time to oxygen saturation (SpO₂) $\geq 94\%$ on room air without further requirement for oxygen therapy. Time to recovery, defined as the time in days from symptom onset to alleviation of all COVID-19 symptoms.

Objectives	Endpoints
Exploratory	

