7.5 Multiple Testing

No adjustments for alpha spending will be performed.

8 Summary of Study Data

All continuous variables will be summarized using the following descriptive statistics: n (non-missing sample size), mean, SD, median, maximum and minimum. The frequency and percentages (based on the non-missing sample size) of observed levels will be reported for all categorical measures.

In general, all data will be listed, sorted by randomized treatment (Placebo, EDP1815) and participant number. If additional sites are added, then data will be sorted by participant number within site. Relevant listings will include whether the assessment was performed and the date, study day/visit and time of the assessment as applicable.

Unless otherwise specified below, all summary tables will be structured with a column for each treatment (placebo, EDP1815) and, for data collected prior to dosing, will include an overall total column where appropriate.

Columns will be ordered and labelled as follows:

- Placebo
- EDP1815
- Total

Except for disposition tables in which it is appropriate to include screened subjects, the enrolled population will be used, otherwise the ITT population will be used for all summaries of disposition, demographic and baseline data and efficacy.

The safety population will be used for all summaries of safety.

Unless otherwise specified, all listings will be produced using the ITT population.

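### Discharged participants with no diary for the day drop out of the OSCI tables although their level is bounded at 0–2, which inflates each arm's percentage at OSCI 3–8

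*SAP*

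**What the plan says.** - **Source of the score.** SAP 5.3.3.4: "Once discharged, the WHO OSCI will be derived from questions 1 and 2 of the daily COVID-19 diary". Table 7 there returns only 0, 1 or 2. Home oxygen does not raise the score: "Note that participants who are discharged on home oxygen will still be considered as having WHO OSCI score =2".
- **What is imputed.** Death gives 8 on all later days. After two consecutive days with no symptoms and a return to usual activities, "the missing WHO OSCI score will be imputed as 0 for any remaining study days up to and including Day 42". For everything else, "WHO OSCI scores that are missing for reasons other than death or full recovery of symptoms will not be imputed". The text under Table 11 (SAP 9.3.3.1) repeats this: "Data missing for reasons other than an intercurrent event as detailed above will not be imputed". The discharge row of Table 11 only points back to the diary derivation.
- **Denominator.** SAP section 8: "The frequency and percentages (based on the non-missing sample size) of observed levels will be reported for all categorical measures".
- **Summary measures.** SAP 9.3.3.1 begins its list with "Percentage of participants at each level of the WHO OSCI score" and adds shifts from baseline, remaining at or below baseline, and worst score. SAP 9.3.3.2 adds a CMH test by day. It describes no sensitivity analysis for missing OSCI.
- **Other information on discharged participants.** SAP 4.2 defines time to discharge as "time in days from start of treatment to first occurrence of a WHO OSCI score of 2 or less". The Schedule of Activities has separate rows for discharge status and mortality status. Protocol 8.1.4 has discharged participants telephoned on Days 7, 14, 21 and 42.
- **When the diary stops.** Protocol 8.1.3 ends it once the participant has been free of symptoms and off oxygen for 48 hours. Return to usual activities is not a condition there.

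**The concern.** Baseline OSCI is 4 or 5 (SAP 7.2), so every discharged participant has moved to a better category. The plan knows that category from the discharge record but discards it when one diary page is missing, because the exact level within 0–2 is unknown. Participants still in hospital are scored daily by the site, so for this reason of missingness the loss falls only on the discharged side of the table.

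The gap is not confined to poor compliance. A participant who stops the diary as protocol 8.1.3 allows, but has not also reported two days of return to usual activities, does not qualify for the imputed 0. That score then stays missing to Day 42, although Table 7 scores a symptom-free day as 0 whatever the answer on interference with activities.

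The SAP deals with discharge elsewhere. It has a discharge rule for S/F ratio (Table 5) and for SpO₂ ≥94% (5.3.3.6), and a missing-diary rule in the pyrexia sensitivity variable (5.3.3.8). OSCI has none.

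The analyses are descriptive, but the pilot is meant to judge endpoints and inform later sample sizes. The OSCI summary and shift tables (14.2.4.1 and 14.2.4.2) also go unblinded to every DMC meeting, and the decision at 60 participants on extending to 100 has no pre-defined rule (SAP 7.4.3).

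**Working it through.** The documents give no expected OSCI distribution, discharge rate or diary-missing rate, so there is no plan figure to reproduce. All rates below are assumptions.

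**1. Within one arm.** Let H be the true share at OSCI 3–8. Let m be the share of discharged participants whose score is missing after the recovery rule has been applied. Everyone else is scored, and those missing are truly at 0–2.

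Planned percentage = H / [H + (1 − H)(1 − m)]; full-denominator percentage = H.

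For H = 20%, m = 30%: 0.20 / (0.20 + 0.80 × 0.70) = 0.20 / 0.76 = 26.3%.

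| True H | m = 10% | m = 20% | m = 30% | m = 40% |
|---|---|---|---|---|
| 10% | 11.0 | 12.2 | 13.7 | 15.6 |
| 20% | 21.7 | 23.8 | 26.3 | 29.4 |
| 30% | 32.3 | 34.9 | 38.0 | 41.7 |
| 40% | 42.6 | 45.5 | 48.8 | 52.6 |

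The overstatement runs from 1.0 point (11.0 − 10) to 12.6 points (52.6 − 40). It is zero only if m = 0 or H is 0 or 100%.

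**2. Between arms.** Take 30 per arm (60 randomised 1:1). Assume 12 on placebo and 6 on EDP1815 at OSCI 3–8, with 18 and 24 discharged. With completion c among the discharged, the planned percentages are 12/(12 + 18c) and 6/(6 + 24c). Differences are taken before rounding.

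| Completion, placebo / EDP1815 | Placebo % | EDP1815 % | Difference (points) |
|---|---|---|---|
| 100 / 100 | 40.0 | 20.0 | 20.0 |
| 70 / 70 | 48.8 | 26.3 | 22.5 |
| 50 / 50 | 57.1 | 33.3 | 23.8 |
| 90 / 50 | 42.6 | 33.3 | 9.2 |
| 50 / 90 | 57.1 | 21.7 | 35.4 |

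With a common c, the odds ratio (placebo to EDP1815) is [12/(18c)] / [6/(24c)] = (12 × 24)/(18 × 6) = 2.67, and c cancels. With no true difference (H = 20% in both arms), m = 10% on EDP1815 and 30% on placebo gives 21.7 − 26.3 = −4.6 points; the reverse gives +4.6.

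**3. Unrecorded readmission or death.** Take one arm of 30 with 6 at OSCI 3–8 and 24 discharged, 6 of those without a score. Planned: 6/24 = 25.0%. With the six set to 2: 6/30 = 20.0%. If a share r of the six is truly at 3–8, the true value is (6 + 6r)/30. This reaches 25.0% at r = 25%, so below that the planned figure is too high. The two figures are equally far from the truth at 22.5%, where r = 12.5%; below that the fix is closer.

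**4. Remaining at or below baseline.** SAP 5.3.3.4 counts a participant as meeting this only if no earlier score was above baseline. It does not say what happens when the score on the day itself is missing. Suppose 5 of 30 have worsened, all observed, and 6 of the other 25 have no diary. Dropping the six gives 19/24 = 79.2%; counting them gives 25/30 = 83.3%.

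**The case against.** Two stronger readings are tempting, and the documents support neither.

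- A reader might infer that the rule works against a treatment that speeds discharge. It need not. Equal completion leaves the odds ratio unchanged and, in the example, widens the difference from 20 to 22.5 or 23.8 points. Unequal completion can shrink it to 9.2 or stretch it to 35.4. Nothing in the documents says which arm would complete more diaries.
- A reader might infer that OSCI is missing only for good outcomes. Participants admitted to ICU may enter another trial and be withdrawn (protocol 7.1), and Table 11 then excludes them. Their data are otherwise collected only where practical. Transfer to another hospital can end in loss to follow-up (protocol 7.4). These losses remove poor outcomes and offset part of the inflation.

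Other points also have weight. Participants who met the two-day rule already score 0 and are not lost, so a raw diary-completion rate would overstate m. The telephone calls prompt diary completion on four of the five OSCI days. Missingness will be visible in Table 14.1.1.4 (data availability by inpatient/outpatient status) and Table 14.1.5.2 (diary compliance). Overall survival is unaffected, and so is time to discharge, which SAP 5.3.3.6 takes from the discharge date. A participant lost after discharge counts as withdrawn, and that person's level is not known.

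These points limit the size and scope but do not remove the problem. Visible missingness does not correct the percentages. The Schedule of Activities marks the 8-point scale at Days 21 and 42, but the SAP gives no rule for using a telephone-visit score in place of a missing diary.

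**Conclusion.** The concern holds within each arm. For participants who are discharged, still in the study, alive and not readmitted, the plan discards a score known to be 2 or lower, and this raises the reported percentage at OSCI 3–8. Over the assumed ranges the excess is 1.0 to 12.6 points, and 6.3 points at H = 20% and m = 30%. The actual size cannot be known from the documents, and missing poor outcomes may partly offset it. The mismatch between the protocol's stopping rule and the SAP's recovery condition adds to m even when participants comply.

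The percentages by level, the shift tables and the by-day CMH test are affected. The effect on remaining at or below baseline is not settled by the text. No direction of bias between arms can be claimed: differential completion can move the difference either way. The change is worth making before database lock, because the rule discards information the study already collects.

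**What to change.** In SAP 5.3.3.4, with a matching line under Table 11:

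1. Apply the recovery rule first. Then, if a participant is discharged, still in the study (not withdrawn or lost to follow-up), has no recorded death or readmission, and has no diary for the day, set OSCI to 2, the worst ambulatory level, for that day.
2. For remaining at or below baseline, count such a participant as meeting the endpoint only if no earlier score was above baseline.
3. Add a sensitivity analysis carrying forward the last diary score.
4. Align the SAP condition for imputing 0 with the protocol's diary-stopping rule, so that participants who stop as instructed are not left missing.

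The cost is one derivation rule, one sensitivity output and a wording alignment, with no new data collection. The downside is that levels 0–2 are slightly blurred, since some participants truly at 0 or 1 will be shown at 2. The rule also relies on readmissions and deaths being recorded; step 3 of the working shows how far unrecorded ones would matter.
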